5.4 Harm

5.4.1 General consideration

Patients with IHCA have an in-hospital mortality of 70 to 75% and many patients experience post-cardiac arrest complications such as global brain injury, impaired myocardial function, macrocirculatory failure, acute respiratory distress syndrome, and increased susceptibility to infections.^{26,93} Furthermore, patients suffering from IHCA often have multiple underlying conditions including heart failure, myocardial infarction, respiratory insufficiency, diabetes, infections, and renal insufficiency.⁹⁴ The immediately preceding cause might be related to circulatory failure (e.g. cardiogenic shock, sepsis), respiratory failure (e.g. pneumonia, chronic obstructive pulmonary disease), arrhythmias (e.g. primary arrhythmias, myocardial infarction), or in in rare instances neurological disorders.⁹⁵⁻⁹⁸ Given this, it is difficult, if not impossible, to comprehensively report all adverse events and assess their possible relationship with the intervention in this patient population. Sodium bicarbonate is considered safe and is commonly used in clinical practice. The overall benefit and potential harm of the intervention will be captured in our primary and secondary outcomes. Any specific adverse events suspected by the clinical team to be related to the intervention will be documented.

5.4.2 Definitions

The following definitions will be used⁹⁹:

Adverse event: An untoward medical occurrence after exposure to a medicine, which is not necessarily caused by that medicine.

Adverse reaction: A noxious and unintended response to a medicine.

Serious adverse reaction: An adverse reaction that results in death, is life-threatening, requires hospitalization or prolongation of existing hospitalization, results in persistent or significant disability or incapacity, or is a birth defect.

Unexpected serious adverse reaction: A serious adverse reaction, the nature, severity, or outcome of which is not consistent with the reference safety information.

Causality with the trial drug will be determined by the site investigator.

5.4.3 Specific adverse events

Sodium bicarbonate is widely used in critically ill patients across the world with limited side effects. After administration, intravenous sodium bicarbonate rapidly dissociates to form sodium and bicarbonate. Thus, the specific adverse and potentially serious adverse events are primarily related to changes in pH and electrolytes. To assess specific adverse and potentially serious adverse events, we will collect data on the following:^{60,100,101}

- 1) Alkalosis (pH > 7.45)
- 2) Hypernatremia (> 145 mmol/L)
- 3) Severe hypocalcemia (ionized calcium < 0.9 mmol/L)
- 4) Hypokalemia (< 3.5 mmol/L)
- 5) Severely elevated lactate (> 10 mmol/L)

The administration of sodium bicarbonate is known to cause an increase in pH.¹⁰² This could potentially cause pH to increase outside the normal range causing alkalosis. With a normal range for pH of 7.35 to 7.45, alkalosis is defined as pH > 7.45.¹⁰³

BIHCA Protocol – version 1.5 Page **37** of **84** The dissociation of sodium and bicarbonate leads to an increase in sodium levels, which potentially could lead to hypernatremia. With a normal range for sodium of 135-145 mmol/L, hypernatremia is defined as > 145 mmol/L.¹⁰⁴

Hypocalcemia has been observed following sodium bicarbonate administration. This is mediated through an increase in pH which changes the binding between ionized calcium and proteins, and through a direct binding between bicarbonate and calcium.¹⁰⁵ With a normal range for ionized calcium of 1.17-1.33 mmol/L, hypocalcemia is defined as ionized calcium < 0.9 mmol/L.^{106,107} This definition of hypocalcemia is based on a previous clinical trial in critically ill patients randomized to sodium bicarbonate or placebo.⁶³

A reduction in the serum potassium level has been observed following sodium bicarbonate administration in patients.¹⁰⁰ With a normal range for potassium of 3.5 to 5.0 mmol/L, hypokalemia is defined as < 3.5 mmol/L.¹⁰⁸

An increase in lactate levels has been observed following sodium bicarbonate administration in experimental studies.¹⁰⁹ Normal lactate levels are 0.6 to 1.4 mmol/L.¹¹⁰ However, as patients resuscitated from IHCA have elevated lactate levels (the median lactate level in the VAM-IHCA trial was 10 [first and third quartile: 7, 13]), severely elevated lactate is defined as > 10 mmol/L.¹¹¹

Other potential side effects have been described with the administration of sodium bicarbonate, including headache, muscle pain, nausea and vomiting, and vertigo.^{60,101} However, given that patients with cardiac arrest are unconscious, these cannot be assessed and are of limited relevance.

Accidental subcutaneous injection of sodium bicarbonate can result in tissue necrosis.¹¹² However, the trial drug is given immediately after adrenaline, which carries a similar risk and hence the same precautions; a misplaced peripheral catheter should be recognized here. The risk of necrosis due to the intervention is therefore minimal.

5.4.4 Collection and timeline

The listed adverse events are assessed using routinely collected data in patients with IHCA. This includes available laboratory values and clinical data. No specific procedures or blood draws will be performed. Based on previous data from the VAM-IHCA trial, the data needed to assess these adverse events are available in all patients achieving ROSC.³⁴ The specific adverse events will only be collected in patients with ROSC.

The physiological effects of sodium bicarbonate administration during cardiac arrest are likely to be short-lived. After administration, intravenous sodium bicarbonate rapidly dissociates to form sodium and bicarbonate. Bicarbonate anions can consume hydrogen ions (H^+) and subsequently convert to carbonic acid (H_2CO_3 , see section 1.2.1). Carbonic acid subsequently converts to water (H_2O) and carbon dioxide (CO_2) for excretion from the lungs. This process occurs within minutes and the concomitant effect on electrolytes

BIHCA Protocol – version 1.5 Page **38** of **84** disappear within 24 hours.¹¹³ As such, the specific adverse events listed in section 5.4.3 will only be assessed within the first 24 hours.

5.4.5 Suspected Unexpected Serious Adverse Reaction (SUSAR)

Suspected Unexpected Serious Adverse Reactions (SUSAR) will be reported to the independent datamonitoring committee (IDMC) (see section 10.2) and the regulatory authorities through EudraVigilance. Given the consideration outlined in section 5.4.1, most events or conditions, including but not limited to organ failure, infection, tissue ischemia, brain damage, cardiac arrest, and death, will not be considered SUSARs. This approach is compatible with previous and ongoing trials by our group (EudraCT numbers: 2017-004773-13, 2019-003387-46, and 2021-005922-82). No events, including those outlined in section 5.4.3, will automatically lead to unblinding.

5.4.6 Reporting

Serious adverse events will be reported to the sponsor within 24 hours.

No later than 15 days thereafter, the sponsor will notify the regulatory agencies through Clinical Trials Information System (CTIS) when the trial has started, when the first subject is included, when recruitment has ended, and when the trial has ended. Similarly, the sponsor will notify the regulatory agencies through CTIS in case of a temporary halt of the trial and in case of any serious breach. Once a year, the sponsor will submit a list of all registered adverse events that have occurred during the trial period as a well as a report on safety of the trial subjects to the regulatory agencies through CTIS. The results from the clinical trial, including important adverse events, will be recorded on CTIS no later than one year after the end of the trial.

5.4.7 Drug interactions

Sodium bicarbonate administration is recommended in patients with selected toxic ingestions.¹¹⁴ The potential mechanisms of sodium bicarbonate in this context is alkalization of urine and subsequent increased urinary excretion of the ingested drug. This increased excretion could potentially result in lower plasma concentrations of selected drugs. However, given the severity of the metabolic acidosis in patients with IHCA, the volume of sodium bicarbonate administered in the current trial is unlikely to result in alkalization of urine and subsequent increased urinary excretion of selected drugs.

5.5 Additional follow-up

The primary trial and publication will be related to the trial outcomes (section 5.1, 5.2, and 5.3). However, extended follow-up at six months and at one year, including overall survival, neurological outcomes, and health-related quality of life, will be collected, and reported in a separate publication. Data will be collected and analyzed like the 90-day outcomes and will be reported in a separate publication. Although the overall trial will be unblinded after the collection of the 90-day outcomes, the person assessing six months and one-year outcomes will be blinded to the treatment assignment.

6. SAMPLE SIZE CALCULATION AND STATISTICAL ANALYSIS PLAN

6.1 Sample size calculation

The trial will be powered to the primary outcome of ROSC. From the VAM-IHCA trial, which had similar inclusion and exclusion criteria, the proportion of patients with ROSC in the placebo group was 33%.³⁴ Based on an absolute difference of 10% between the placebo and the bicarbonate group, we anticipate that 33% in the placebo group and 43% in the intervention group will obtain ROSC. This corresponds to a relative increase of 30%. With such estimates, an alpha of 0.05, and the use of the Fisher's Exact test, we will need a total of 778 patients to have 80% power to detect a statistically significant difference between groups. Given that the primary analysis will be adjusted for strong prognostic factors (see section 6.2.2 and 6.2.4), we will obtain additional power.^{115,116} The trial therefore has a minimum of 80% power.

We anticipate no loss to follow-up for the primary outcome (see section 6.2.7). Patients who withdraw consent and request deletion of data will not be replaced. Of note, no patients withdrew consent in our previous trials.^{34,54}

6.2 Statistical analysis plan

6.2.1 General considerations

Details related to the statistical analysis plan are included in the present protocol and there will be no separate document.

Patient inclusion and exclusion will be illustrated in a CONSORT flow diagram (see Appendix 2 for a draft). All analyses will be conducted on a modified intention-to-treat basis only including patients receiving the first dose of the trial drug and meeting all inclusion criteria and no exclusion criteria. In a double-blind trial, where the inclusion and exclusion criteria are documented (but might not be known by the cardiac arrest team) prior to the cardiac arrest and the intervention, this approach is unbiased while increasing precision.¹¹⁷ The two groups will be compared in relation to baseline patient and cardiac arrest characteristics using descriptive statistics (See Appendix 3 for a draft of the Table 1).

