5. OUTCOMES

5.1 Primary outcome

5.1.1 Definition

The primary outcome will be ROSC. ROSC will be defined as spontaneous circulation with no further need for chest compressions sustained for at least 20 minutes. This definition is consistent with our previous trials^{34,54}, the *Get With the Guidelines® – Resuscitation* registry⁷³, the Danish registry for IHCA (DANARREST)⁷⁴, and the Utstein guidelines⁷⁵. If a patient is placed on extracorporeal circulation during the cardiac arrest, the patient will only be considered to have ROSC if they are able to be successfully weaned from the extracorporeal circulation with spontaneous circulation for at least 20 minutes.⁷⁶

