6.2.5 Other analyses and considerations

Health-related quality of life and SOFA-scores will only be assessed in those alive at the time of measurement and no imputation will be performed for those not alive at the time of measurement.

Survival until 90 days will be presented graphically with Kaplan-Meier curves,¹²³ but will otherwise be analyzed as a binary outcome as described in section 6.2.2.

Adverse events and categorical outcomes will only be presented descriptively.

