7.2 Variables

7.2.1 Overview

All IHCA patients at the participating sites will be entered into a screening log. For those not randomized, a specific reason for non-inclusion/exclusion will be documented. All randomized patients who received the trial drug will be entered into the main database.

A detailed data dictionary that clearly defines all included variables will be created prior to patient enrollment. The data dictionary will provide the name of the variable (including the code used in the database), a detailed definition of the variable, categories for categorical variables, and units and ranges for continuous variables. The number of collected variables will be kept relatively small to limit resource use and data entry mistakes. The included variables largely include those outlined in the IHCA Utstein guidelines.¹²⁷ Below is provided a brief overview of the included variables but details are reserved for the data dictionary.

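### Specific adverse events have no all-dosed population: under section 6.2.1, patients who received the drug but prove ineligible are left out of the by-arm adverse-event table

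*Protocol*

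**What the plan says.** Section 6.2.1 bases all analyses on a modified intention-to-treat set, "only including patients receiving the first dose of the trial drug and meeting all inclusion criteria and no exclusion criteria". It calls this unbiased and more precise because eligibility is documented before the arrest, even if the team does not know it at the time. The same section says that no separate analysis plan will be written.

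Section 6.2.5 covers how harms are analysed: "Adverse events and categorical outcomes will only be presented descriptively". It names no population for them.

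Section 7.2.1 is wider on data entry: "All randomized patients who received the trial drug will be entered into the main database".

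The five specific adverse events in section 5.4.3 are all laboratory thresholds: pH, sodium, ionized calcium, potassium and lactate. Section 5.4.4 limits who contributes them, "The specific adverse events will only be collected in patients with ROSC", and when: they "will only be assessed within the first 24 hours". Section 5.1.1 defines ROSC as "spontaneous circulation with no further need for chest compressions sustained for at least 20 minutes". For a patient placed on extracorporeal circulation during the arrest it adds that "the patient will only be considered to have ROSC if they are able to be successfully weaned from the extracorporeal circulation", again with at least 20 minutes of spontaneous circulation.

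**The concern.** A harm table normally covers everyone exposed to the drug. Here the efficacy set also governs the harm table, so some exposed patients are left out by rule. The protocol expects such patients: section 6.2.1 accepts that the team may not know the criteria, and section 4.3 accepts that resuscitation is sometimes started despite a do-not-resuscitate order.

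The justification in section 6.2.1 concerns effect estimates. It does not explain why a descriptive table of events among exposed patients should omit some of them. What is at stake is the completeness of the only by-arm final report of the five events. The validity of the treatment comparison is not in question.

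**Working it through.** **1. Scope of the analysis set.** The sentence in section 6.2.1 states its own scope: "All analyses will be conducted on a modified intention-to-treat basis only including patients receiving the first dose of the trial drug and meeting all inclusion" (the quotation stops short here; the rest of the sentence completes the eligibility conditions). Section 6.2.5 makes no exception for adverse events, and no safety set is defined elsewhere. The protocol says it contains the whole analysis plan, so this is a stated rule and not a detail left for later.

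**2. Who is in the database but not in the table.** The database in section 7.2.1 holds patients who were randomized and dosed. The table holds those who were dosed, met all inclusion criteria, met no exclusion criterion and had ROSC. The difference has two parts:

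- Dosed patients later found ineligible. They are in the database and in no final analysis.
- Dosed, eligible patients without ROSC as section 5.1.1 defines it. Most of these die during the arrest. A patient who leaves resuscitation on extracorporeal circulation and is never weaned is also in this group, and may be alive with blood gases taken inside the 24-hour window.

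**3. The plan's own figures.** The total of 778 (389 per arm, 33% vs 43% ROSC, two-sided 0.05, Fisher's exact test) reproduces, with exact power of 80.2% at 389 per arm. It is not in dispute and serves only as a base. Expected patients with ROSC, and so with specific adverse-event data:

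- Placebo: 389 × 0.33 = 128.4
- Bicarbonate: 389 × 0.43 = 167.3
- Total: 295.6, which is 38% of 778

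**4. Size of the ineligible group.** The documents give no rate, so the share q of dosed patients who prove ineligible is an assumption.

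| q | If 778 counts all dosed: 778 × q | If 778 counts those analysed: 778 × q/(1 − q) |
|---|---|---|
| 1% | 7.8 | 7.9 |
| 3% | 23.3 | 24.1 |
| 5% | 38.9 | 40.9 |
| 10% | 77.8 | 86.4 |

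Only those with ROSC would have event data. Assume further that ineligible patients reach ROSC at the planned rates. The low end is then 7.8 × 0.33 = 2.6 and the high end, at q = 5%, is 40.9 × 0.43 = 17.6. That is about 3 to 18 patients, against roughly 296 in the table.

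**5. Extracorporeal circulation.** A number here would need both the rate of its use and the share never weaned. The documents give neither, so none is offered. The data needed are largely in hand: section 7.2.3 lists laboratory values for the first 24 hours without a ROSC condition, and item 19 of the registry form in Appendix 4 has its own category for resuscitation that ended with artificial circulation.

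**The case against.** The strongest reply is that little is lost. Eligibility is settled before a blinded intervention, so the removal should be balanced between arms. The table carries no test, so no trial conclusion depends on it. The numbers rest on assumed rates, and the one related figure in section 4.3, one pregnancy among 2,362 patients assessed in the previous trial, points low for that criterion. All of this stands. It limits the point to completeness and makes it small.

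Several stronger readings are tempting, and the documents do not support them:

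- *These patients vanish from all harm reporting.* They do not. Section 5.4.1 documents events that the clinical team suspects are related. Sections 5.4.5 and 5.4.6 cover SUSARs, serious adverse events and a yearly list of registered events. None of these states an eligibility or ROSC condition. They do not replace a by-arm table of the five events, however.
- *Patients on extracorporeal circulation have no safety data.* Those weaned with 20 minutes of spontaneous circulation count as ROSC. A never-weaned eligible patient stays in the ROSC, survival and neurological outcomes, which section 5.4.1 names as the overall capture of benefit and harm. Section 5.3 also compares first-gas values between groups without a stated ROSC condition. Only the thresholded events are missing.
- *The IDMC sees a much wider adverse-event denominator.* The file in Appendix 5 has a row for each patient who entered the trial, but its single event flag uses the section 5.4.3 events, which are collected only after ROSC. It can differ only by ineligible patients with ROSC.
- *Unrecognised pregnancies would be removed.* The criterion is known or suspected pregnancy, so an unrecognised one does not breach it.
- *Prior enrollees are excluded because repeat exposure is a hazard.* Section 4.3 gives correlated data as the reason, and the first enrollment remains analysed.

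**Conclusion.** The point holds in limited form. As written, section 6.2.1 keeps dosed patients later found ineligible out of the by-arm table of specific adverse events, although their data are held. Nothing in the protocol justifies this for harms. It leaves the exposed population incompletely reported and is not a bias between arms.

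The number is probably small: about 8 to 41 exposed patients if 1 to 5% of those dosed prove ineligible, and about 3 to 18 with event data if they reach ROSC at the planned rates. Both rates are assumptions without support in the documents. The extracorporeal gap is secondary, confined to never-weaned patients, and cannot be sized. Sample size and efficacy analyses are unaffected.

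**What to change.** Add to section 6.2.1:

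*Specific adverse events will be reported descriptively for all patients who received any trial drug, regardless of eligibility; the modified intention-to-treat set applies to the efficacy outcomes. A patient enrolled more than once is counted once, in the arm of the first kit, and events after a second kit are listed separately.*

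The last sentence is needed because a rule based only on drug received would not say where to place a patient given bicarbonate from one kit and placebo from another.

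Optionally, extend section 5.4.4 so that the five events are also derived, from laboratory values already collected, for patients whose resuscitation ended on extracorporeal circulation.

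The cost is data entry for a few more patients, and harm and efficacy tables with different denominators, which a footnote can explain. No extra blood draws or procedures are needed.

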6.2.2 Binary outcomes

Binary outcome variables will be presented as counts and proportions in each group. Differences between groups will be presented as risk ratios and risk differences. Risk ratios and risk differences will be estimated using generalized linear models. The risk ratio will be estimated from a log-binomial regression model (i.e., binomial distribution and log link function).¹¹⁸ If this model fails to converge, a modified Poisson regression model will be used instead (i.e., Poisson distribution and log link function).¹¹⁸ If this model fails to converge, a modified Poisson regression model will be used instead (i.e., Poisson distribution and log link function with robust standard errors).^{118,119} The risk difference will be estimated using a linear model (i.e., binomial distribution and identity link function). If this model fails to converge, an equivalent modified Poisson approach will be used.¹¹⁸

To increase power, all models will include adjustment for strong prognostic factors (see section 6.2.4). If the models are not able to converge with the inclusion of these variables, the adjustment will be done using inverse probability of treatment weighting.¹²⁰ In case none of these models are feasible, 95% confidence intervals will be obtained using methods described by Miettinen and Nurmimen.¹²¹

6.2.3 Continuous outcomes

Continuous data will be presented as means with standard deviations (SD) or medians with first and third quartiles depending on the distribution of the data. Differences between groups in continuous outcomes are presented as mean differences with 95% confidence intervals obtained from a generalized linear model with robust errors with adjustment for prognostic variables (see section 6.2.4). If the data are severely non-normally distributed, other methods (e.g., transformation of the outcome, quantile regression, Hodges–Lehmann median difference) will be considered or the data will be presented descriptively.

6.2.4 Adjustment for prognostic factors

To increase power, we will adjust all outcome comparisons for strong prognostic factors.^{115,116} These will include age, whether the cardiac arrest was witnessed, and the initial rhythm. Age will be included as a linear continuous variable¹²² and the initial rhythm (shockable [ventricular fibrillation or ventricular tachycardia] or non-shockable [asystole or pulseless electrical activity]) and witnessed status as binary variables. A recent meta-analysis found that these variables are strongly associated with survival after IHCA.²⁵ To confirm that these variables are also strongly correlated to ROSC and other relevant outcomes in the Danish setting, we performed multivariable logistic regression with age, witnessed status, and initial rhythm as the independent

variables and various outcomes as the dependent variable using data from the VAM-IHCA trial (n = 501).³⁴ As can be seen in Table 3, these variables were strongly associated with outcomes.

Variable	Odds ratio (95%CI)					
	ROSC	30-day survival	30-day favorable			
		So-day Survivar	outcome (mRS 0-3)			
Age (per 10-year increase)	0.88 (0.70, 0.95)	0.67 (0.54, 0.82)	0.63 (0.49, 0.81)			
Non-witnessed vs. witnessed	0.50 (0.32, 0.79)	0.18 (0.06, 0.60)	0.26 (0.06, 1.11)			
Non-shockable vs. shockable	0.46 (0.25, 0.83)	0.35 (0.17, 0.72)	0.31 (0.13, 0.75)			

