3. TRIAL DESIGN

3.1 Overview

This is an investigator-initiated, multicenter, randomized, placebo-controlled, parallel group, double-blind, superiority trial of sodium bicarbonate during adult IHCA. There will be 21 enrolling sites in Denmark. 778 adult patients with IHCA receiving at least one dose of adrenaline will be enrolled. The primary outcome is ROSC and key secondary outcomes include survival at 30 days and survival at 30 days with a favorable neurological outcome.

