3.2 Allocation

Patients will be randomized in a 1:1 ratio to either sodium bicarbonate or placebo in blocks with random sizes of 2, 4, or 6. The randomization will be stratified according to site.⁶⁹ An independent statistician will create the randomized allocation list using a random number generator. The list will only be shared with the pharmacy, which will not be involved in clinical care. The pharmacy and the independent statistician will both store the randomization list. As described in section 3.3 and section 3.4, sites will be provided with numbered blinded kits including either sodium bicarbonate or placebo ensuring allocation concealment.

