6.2.6 Subgroup analyses

Subgroup analyses will be performed on both the absolute and relative scale using risk ratios and risk differences as described in section 6.2.2.¹²⁴ These analyses will not include adjustment for prognostic variables. The analyses will include five pre-defined subgroup analyses for the primary and key secondary outcomes according to 1) first documented rhythm, 2) whether the cardiac arrest was witnessed, 3) patient age, 4) time from cardiac arrest to first trial drug, and 5) known metabolic acidosis prior to the cardiac arrest. The first documented rhythm will be dichotomized as shockable or non-shockable. Patient age and time from cardiac arrest to first trial drug will be dichotomized by the median. As a secondary analysis, these variables will be treated as linear, continuous variables and the results illustrated graphically. Known metabolic acidosis prior to the cardiac will be defined as a pH < 7.35 and a base excess < -2 mmol/L based on the latest laboratory values prior to the cardiac arrest. Only blood samples taken within 6 hours of the cardiac arrest will be considered.

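### Randomisation is stratified by site but no analysis accounts for site, so the reported standard errors are slightly too large whenever ROSC differs between hospitals

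*Protocol*

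**What the plan says.** Section 3.2 (Allocation) randomises 1:1 "in blocks with random sizes of 2, 4, or 6" and states: "The randomization will be stratified according to site". No other stratification factor is named. Section 3.1 (Overview) gives the number of strata: "There will be 21 enrolling sites in Denmark".

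Section 6.2.4 (Adjustment for prognostic factors) sets the covariates for all outcome comparisons: "These will include age, whether the cardiac arrest was witnessed, and the initial rhythm". It then codes these three variables and supports them with a regression table containing the same three. Sections 6.2.2 (binary outcomes) and 6.2.3 (continuous outcomes) refer back to this list. Section 6.2.6 (Subgroup analyses) drops even these: "These analyses will not include adjustment for prognostic variables".

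Site does not appear in section 6.2 as a fixed effect, random effect, stratum or cluster term, and no reason is given. Section 6.2.1 says that the protocol holds the full analysis plan and that no separate one will be written, so the choice is not deferred. Site is a collected variable (section 7.2.2).

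**The concern.** Permuted blocks within site balance the arms within each hospital. If hospitals differ in ROSC, that variation largely cancels from the comparison between arms. A model without site leaves it in the residual, so its SE describes a trial randomised without stratification. The interval is then wider than it needs to be, and the test rejects less often than its nominal level.

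ROSC is the first outcome in the testing hierarchy of section 6.2.8, so power given up there is also given up for 30-day survival and for favourable neurological outcome. The plan adjusts for covariates in order to gain power, and the factor it stratified on is a natural candidate for the same treatment.

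**Working it through.** **Inputs from the protocol.** ROSC 33% vs 43%, alpha 0.05, 80% power, total 778 (section 6.1); two-sided tests (6.2.8); 21 sites, so 778 / 21 ≈ 37 patients per site on average; blocks of 2, 4 or 6 within site (3.2); covariate odds ratios from Table 3 (6.2.4).

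**Assumed.** The between-site ICC for ROSC, taken over 0 to 0.10. In the simulations, also the site sizes and the covariate prevalences.

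**Step 1: the plan's own figure.** The two-proportion formula without continuity correction gives 369 per arm (738 in total). The correction n′ = (n/4)·[1 + √(1 + 4/(nΔ))]² with n = 369 and Δ = 0.10 gives 388.8, rounded up to 389 per arm, 778 in total. Enumerating the two-sided Fisher test at 389 per arm gives exact power of 80.2%. The stated figure is reproduced. It comes from an unadjusted test and does not depend on how site is handled.

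**Step 2: effect on the SE and the test.** If site is balanced by design but left out of the model, the reported variance is too large by about 1/(1 − ICC). So:

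- SE ratio = 1/√(1 − ICC)
- true two-sided type I error = 2·[1 − Φ(1.96/√(1 − ICC))]

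**Step 3: power.** At 389 per arm the pooled SE is √(2 × 0.38 × 0.62 / 389) = 0.0348 and the unpooled SE is 0.0346. Power by the uncorrected normal approximation is Φ((0.10 − 1.96 × 0.0348)/0.0346) = 82.1%. With site in the model both SEs are multiplied by √(1 − ICC). Without site only the true spread (the denominator) shrinks, while the reported SE does not.

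| Assumed ICC | SE too large by | True type I error | Power with site | Gain over 82.1% | Power without site, true spread credited | Gain on that basis |
|---|---|---|---|---|---|---|
| 0 | 0% | 5.0% | 82.1% | 0 | 82.1% | 0 |
| 0.01 | 0.5% | 4.9% | 82.5% | 0.4 points | 82.2% | 0.3 points |
| 0.02 | 1.0% | 4.8% | 82.8% | 0.8 points | 82.3% | 0.5 points |
| 0.05 | 2.6% | 4.4% | 84.0% | 1.9 points | 82.7% | 1.3 points |
| 0.10 | 5.4% | 3.9% | 85.9% | 3.8 points | 83.3% | 2.5 points |

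The gain over 82.1% is an upper figure, because it gives the model without site no credit for the smaller true spread.

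**Step 4: simulation.** 778 patients, 21 unequal sites, blocks within site, risk difference from a linear model with robust SE and the three covariates; 8,000 null and 4,000 alternative runs per setting.

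| ICC | Mean reported SE under the null, without / with site | Empirical SE, without / with | Type I error, without / with | Power, without / with |
|---|---|---|---|---|
| 0 | 0.0331 / 0.0332 | 0.0332 / 0.0332 | 5.2 / 5.2% | 82.9 / 83.0% |
| about 0.05 | 0.0332 / 0.0324 | 0.0324 / 0.0324 | 4.4 / 4.9% | 83.3 / 84.7% |
| about 0.10 | 0.0332 / 0.0316 | 0.0316 / 0.0315 | 3.8 / 4.9% | 85.3 / 87.7% |

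The simulated gains of 1.4 and 2.4 points match the last column of the first table. The empirical SE hardly changes when site is added; only the reported SE does.

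**Step 5: can the planned models carry site?** The models of section 6.2.2 were fitted to simulated trials of the same kind, 200 per setting. Failure means non-convergence or fitted risks outside 0 to 1. For a between-site SD of 0.25 / 0.4 / 0.6 on the logit scale:

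- Log-binomial: about 4% failed without site; 59 / 70 / 84% failed with site indicators.
- Identity-binomial: 0 to 2% failed without site; 75 / 85 / 95% failed with site indicators.

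Under other assumed site sizes the log-binomial with site failed in about 72 to 92% of trials. Poisson with robust SE and site terms converged in all or nearly all; the rare failure is to be expected when a small site has no ROSC event.

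**The case against.** The best case for leaving the plan alone is that the effect is conservative and often negligible. At an ICC of 0.02 or below the SE is off by about 1% or less, and nothing in the documents shows that Danish hospitals differ more than that. The models as written fit reliably. Site indicators would usually push the primary analysis off its first-choice models and into the fallback chain. Both points stand. They limit the size of the concern and rule out the simplest remedy, but they do not explain why the stratification factor is ignored.

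Section 6.2.4 could also be read as an open list. The coding and the supporting table cover exactly three variables, however, and nothing elsewhere adds site. If the list were open, the primary model would not be fully specified.

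A reader might infer more than the documents support:

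- *The benefit of stratifying is thrown away.* It is not. The estimate's actual spread is almost the same with or without site; only its reported precision is understated.
- *The power claim fails.* It does not. The 778 rests on an unadjusted Fisher test with exact power of 80.2%.
- *The plan contradicts its own source.* One reference cited for adjustment has a title about centre effects in multicentre trials with a binary outcome. A title does not show that the source calls for adjustment in this setting.

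**Conclusion.** The concern holds, as a small and conservative inefficiency. The trial stratifies by site and analyses as though it had not. For an assumed ICC of 0.01 / 0.05 / 0.10, the reported SE is about 0.5 / 2.6 / 5.4% too large and true type I error is about 4.9 / 4.4 / 3.9%. About 0.4 / 2 / 4 points of power are forgone at most, or about 0.3 / 1.3 / 2.5 once the smaller true spread is credited. If hospitals do not differ, nothing is lost.

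There is no bias in the risk difference, no inflated type I error and no effect on the sample size. The figures are for ROSC on the risk-difference scale and rest on an ICC that the documents do not give; the 30-day outcomes were not quantified. The case for change is that accounting for site uses data already collected and, in the simulation with no site variation, cost essentially no power.

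**What to change.** Amend sections 6.2.2 and 6.2.4 so that the primary and key secondary analyses account for site, with models named directly:

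- **ROSC, risk ratio:** modified Poisson regression with robust SE and site terms, keeping age, witnessed status and rhythm.
- **ROSC, risk difference:** linear (identity-link) model with robust SE and site terms, and the same three covariates.
- **30-day survival and 30-day favourable neurological outcome:** a random site intercept, or a rule fixed in advance for pooling small sites. Some sites are likely to have few or no events. The same rule should cover any site without a ROSC event.

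Site indicators should not be added to the log-binomial or identity-binomial models. A site-stratified Mantel-Haenszel analysis is not a full substitute, because it drops the three prognostic covariates, and as a supportive analysis it would leave the primary test unchanged.

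The cost is more than one added sentence. The log-binomial gives way as first-choice model for the risk ratio, the identity-binomial does the same for the risk difference, the fallback order must be rewritten to match, and the pooling rule must be set before unblinding. No new data or operational change is needed. If the sponsor prefers to leave site out, the protocol should say so and give the reason.
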